7.5.2. Instructions for Reporting Special Situations

7.5.2.1. Instructions for Reporting Pregnancies

The investigator should report pregnancies in female study subjects that are identified after initiation of study medication and throughout the study, including the post study drug follow-up period, to the or Gilead PVE using the pregnancy report form within 24 hours of becoming aware of the pregnancy.

Refer to Section 7.3 and the eCRF completion guidelines for full instructions on the mechanism of pregnancy reporting.

The pregnancy itself is not considered an AE nor is an induced elective abortion to terminate a pregnancy without medical reasons.

Any premature termination of pregnancy (eg, a spontaneous abortion, an induced therapeutic abortion due to complications or other medical reasons) must be reported within 24 hours as an SAE. The underlying medical reason for this procedure should be recorded as the AE term.

A spontaneous abortion is always considered to be an SAE and will be reported as described in Section 7.1.2. Furthermore, any SAE occurring as an adverse pregnancy outcome post study must be reported to Gilead PVE.

The subject should receive appropriate monitoring and care until the conclusion of the pregnancy. The outcome should be reported to or Gilead PVE using the pregnancy outcome report form. If the end of the pregnancy occurs after the study has been completed, the outcome should be reported directly to Gilead PVE. Gilead PVE contact information is as follows:

Email: PPD [REDACTED]

Fax: PPD [REDACTED]

Pregnancies of female partners of male study subjects exposed to Gilead study drugs must also be reported and relevant information should be submitted to Gilead PVE using the pregnancy and pregnancy outcome forms within 24 hours. Monitoring of the subject should continue until the conclusion of the pregnancy. If the end of the pregnancy occurs after the study has been completed, the outcome should be reported directly to Gilead PVE, fax number PPD [REDACTED] or email PPD [REDACTED]

Refer to Appendix 4 for Pregnancy Precautions, Definition for Female of Childbearing Potential, and Contraceptive Requirements.

7.5.2.2. Reporting Other Special Situations

All other special situation reports must be reported on electronic special situations report form and transmitted to Gilead PVE within 24 hours of the investigator becoming aware of the situation. If for any reason it is not possible to record the special situation report (SSR) information electronically, i.e., the eCRF database is not functioning, record the SSR on the paper special situation reporting form and submit within 24 hours to:

Gilead PVE: Fax: PPD

Email: PPD

As soon as it is possible to do so, any SSR reported via paper must be transcribed into the eCRF database according to instructions in the eCRF completion guidelines. These reports must consist of situations that involve study drug(s) and/or Gilead concomitant medications, but do not apply to non-Gilead concomitant medications.

Special situations involving non-Gilead concomitant medications does not need to be reported on the special situations report form; however, for special situations that result in AEs due to a non-Gilead concomitant medication, the AE should be reported on the AE form.

Any inappropriate use of concomitant medications prohibited by this protocol should not be reported as “misuse,” but may be more appropriately documented as a protocol deviation.

Refer to Section and the eCRF completion guidelines for full instructions on the mechanism of special situations reporting.

All clinical sequelae in relation to these special situation reports will be reported as AEs or SAEs at the same time using the AE eCRF and/or the SAE report form. Details of the symptoms and signs, clinical management, and outcome will be reported, when available.

8. STATISTICAL CONSIDERATIONS

8.1. Analysis Objectives and Endpoints

8.1.1. Analysis Objectives

The primary objectives of this study are as follows:

- To evaluate the antiviral efficacy of therapy with SOF/VEL FDC for 12 weeks and SOF/VEL/VOX FDC for 12 weeks as measured by the proportion of subjects with SVR12
- To evaluate the safety and tolerability by review of the accumulated safety data

The secondary objectives of this study are as follows:

- To determine the proportion of subjects who attain SVR at 4 weeks after cessation of treatment (SVR4)
- To evaluate the proportion of subjects with virologic failure
- To evaluate the emergence of viral resistance to SOF, VEL and VOX during treatment and after cessation of treatment

8.1.2. Primary Endpoint

The primary efficacy endpoint for the study is SVR12 (HCV RNA < LLOQ 12 weeks after discontinuation of study treatment) in the Full Analysis Set (FAS) population.

The primary safety endpoint is any AE leading to permanent discontinuation of study drugs.

8.1.3. Secondary Endpoint

Secondary endpoints include the following:

- The proportion of subjects with SVR4 (HCV RNA < LLOQ 4 weeks after discontinuation of study treatment)
- The proportion of subjects with virologic failure
- The proportion of subjects with HCV RNA < LLOQ on treatment
- HCV RNA change from baseline
- ALT normalization

8.2. Analysis Conventions

All individual subject data will be listed as measured. All statistical summaries and analyses will be performed using SAS[®] software (SAS Institute, Cary, North Carolina, USA).

The study drugs in this study include SOF/VEL FDC and SOF/VEL/VOX FDC. Last dose of study drug refers to the last dose of SOF/VEL FDC (Cohort 1) or SOF/VEL/VOX FDC (Cohort 2) and will be used in the definition of treatment-emergent AEs and laboratory abnormalities as well as the efficacy endpoints of SVR at various post treatment time points.

8.2.1. Analysis Sets

8.2.1.1. Efficacy

The primary analysis set for efficacy analysis will be the FAS, which includes all enrolled subjects who took at least 1 dose of study drug.

8.2.1.2. Safety

The primary analysis set for safety analyses will be the Safety Analysis Set, which includes all subjects who took at least 1 dose of study drug. Treatment-emergent data will be analyzed and defined as data collected from the first dose of the study drug through the date of last dose of study drug plus 30 days.

8.2.1.3. Pharmacokinetics

The PK Analysis Set will include all subjects who received at least 1 dose of study drug, and have at least 1 nonmissing postdose concentration value for the corresponding analyte in plasma. The analytes of interest may include SOF (and its metabolites GS-566500 and GS-331007), VEL or VOX where applicable.

CCI

8.2.2. Data Handling Conventions

Missing data can have an impact upon the interpretation of the trial data. Other than the endpoints discussed below, values for missing data will not be imputed.

For the analyses of categorical HCV RNA data, missing posttreatment HCV RNA data will have the missing data imputed. Missing on-treatment HCV RNA will have the missing data imputed up to the time of the last dose.

If a data point is missing and is preceded and followed in time by values that are “< LLOQ target not detected (TND),” then the missing data point will be set to “< LLOQ TND.” If a data point is missing and preceded and followed by values that are “< LLOQ detected,” or preceded by “< LLOQ detected” and followed by “< LLOQ TND,” or preceded by “< LLOQ TND” and followed by “< LLOQ detected,” then the missing value will be set to “< LLOQ detected.” In these situations, the data point will be termed a bracketed success; otherwise, the data point will be termed a bracketed failure (i.e., \geq LLOQ detected). If a data point is missing and is not bracketed, the missing data point will also be termed a failure (i.e., \geq LLOQ detected).

Where appropriate, safety data for subjects who did not complete the study will be included in summary statistics. For example,

- If a subject took at least 1 dose of study drug, the subject will be included in a summary of AEs according to the treatment received; otherwise, if the subject is not dosed, then they will be excluded from the summary.
- If safety laboratory results for a subject are missing for any reason at a time point, the subject will be excluded from the calculation of summary statistics for that time point. If the subject is missing a pre-dose value, then the subject will be excluded from the calculation of summary statistics for the pre-dose value and the change from pre-dose values.

Values for missing safety laboratory data will not be imputed; however, a missing baseline result will be replaced with a screening result, if available. If no pre-treatment safety laboratory value is available, the baseline value will be assumed to be normal (i.e., no grade [Grade 0]) in the summary of graded laboratory abnormalities. Values for missing vital signs data will not be imputed; however, a missing baseline result will be replaced with a screening result, if available.

HCV RNA values below the LLOQ for the assay will be set to the lower limit minus 1 for calculation of summary statistics for the actual HCV RNA values and the change from baseline values by study visit. The reported values will be provided in the HCV RNA listing.

For selected analyses of early time point data, HCV RNA data (IU/mL) may be transformed to the logarithmic (base 10) scale (\log_{10} IU/mL).

CCI

CCI

8.3. Demographic Data and Baseline Characteristics

Demographic and baseline characteristics will be summarized using standard descriptive methods by cohort.

Demographic data will include sex, self-identified race/ethnicity, and age.

Baseline characteristics data will include BMI, HCV RNA level (\log_{10} IU/mL), genotype of HCV infection, IL28B genotype, and additional endpoints as necessary

8.4. Efficacy Analysis

8.4.1. Primary Analysis

The primary efficacy endpoint for this study will be the proportion of subjects with SVR12 in all enrolled and treated subjects. The primary analysis will be performed after all enrolled subjects have been followed through 12 weeks posttreatment or discontinued from study. The point estimate with a 2-sided 95% exact confidence interval (CI) using the binomial distribution (Clopper-Pearson method) will be constructed for the SVR12 rate by cohort. No hypothesis testing will be performed.

8.4.2. Secondary Analyses

The proportion of subjects with HCV RNA below LLOQ over time (including SVR endpoints) will be presented in tabular and graphical form.

Descriptive summaries and listings will be provided for additional efficacy evaluations of the proportion of subjects who experience virologic failure, ALT normalization, serum HCV RNA actual values and change from baseline. Continuous endpoints will be summarized using an 8-number summary (n, mean, standard deviation [SD], median, Q1, Q3, minimum, and maximum) by cohort. Categorical endpoints will be summarized by number and percentage of subjects who meet the endpoint definition by cohort.

CCI

Details on efficacy analyses will be described in the statistical analysis plan.

8.5. Safety Analysis

Safety endpoints will be evaluated by assessment of clinical laboratory tests, physical examinations, vital signs measurements at various time points during the study, and by documentation of AEs.

All safety data collected on or after the first dose of study drug administration and up to 30 days after the last dose of study drug will be summarized by cohort.

8.5.1. Extent of Exposure

A subject's extent of exposure to study drug will be generated from the study drug administration page of the eCRF. Exposure data will be summarized by cohort.

8.5.2. Adverse Events

Clinical and laboratory adverse events will be coded using the Medical Dictionary for Regulatory Activities (MedDRA). System Organ Class (SOC), High-Level Group Term (HLGT), High-Level Term (HLT), Preferred Term (PT), and Lower-Level Term (LLT) coding will be attached to the clinical database.

Events will be summarized on the basis of the date of onset for the event. A treatment-emergent AE will be defined as any AE with an onset date on or after the date of first dose of study drug and no later than 30 days after permanent discontinuation of the study drug; or any AE leading to premature discontinuation of study drug.

Summaries (number and percentage of subjects) of treatment-emergent AEs (by SOC and PT) will be provided by cohort:

- All AEs
- AEs of Grade 3 or above
- AEs of Grade 2 or above
- All treatment-related AEs
- Treatment-related AEs of Grade 3 or above
- Treatment-related AEs of Grade 2 or above
- All SAEs (including death)
- All treatment-related SAEs
- AEs leading to premature discontinuation of study drug
- AEs leading to interruption of study drug

All AEs collected during the course of the study will be presented in data listings.

8.5.3. Laboratory Evaluations

Selected laboratory data will be summarized (n, mean, SD, median, Q1, Q3, minimum, and maximum) by cohort and study visit along with the corresponding change from baseline.

Graded laboratory abnormalities will be defined using the laboratory toxicity grading scheme in [Appendix 3](#). The incidence of treatment-emergent laboratory abnormalities, defined as values that increase by at least one toxicity grade from baseline at any time postbaseline, up to the date of last dose of study drug plus 30 days will be summarized by cohort.

All laboratory abnormalities will be included in the listings of laboratory data.

8.5.4. Other Safety Evaluations

Individual data for 12-lead ECG and vital sign measurements will be listed by subject and summarized for each cohort and visit by incidence of events/abnormalities or by descriptive statistical summaries (n, mean, SD, median, Q1, Q3, minimum, and maximum), for continuous data by cohort, as appropriate.

8.6. Pharmacokinetic Analysis

In the PK analysis set, concentrations of SOF, its metabolites GS-566500 and GS-331007, VEL, and VOX (as applicable) in plasma will be determined using validated bioanalytical assays and listed. Details of the analyses will be provided in the pharmacokinetic reporting and analysis plan.

CCI

8.7. Sample Size

For Cohort 1, with approximately 50 subjects enrolled into the study, the 2-sided 95% exact CI using the binomial distribution (Clopper-Pearson method) of the SVR12 rate will be from 86.3% to 99.5%, assuming the expected SVR12 rate is 95%.

For Cohort 2, with approximately 30 subjects enrolled into the study, the 2-sided 95% exact CI using the binomial distribution (Clopper-Pearson method) of the SVR12 rate will be from 82.8% to 99.9%, assuming the expected SVR12 rate is 95%.

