1.3. Sample Size and Power

For Cohort 1, with approximately 50 subjects enrolled into the study, the 2-sided 95% exact confidence interval (CI) using the binomial distribution (Clopper-Pearson method) of the SVR12 rate will be from 86.3% to 99.5%, assuming the expected SVR12 rate is 95%.

For Cohort 2, with approximately 30 subjects enrolled into the study, the 2-sided 95% exact CI using the binomial distribution (Clopper-Pearson method) of the SVR12 rate will be from 82.8% to 99.9%, assuming the expected SVR12 rate is 95%.

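### Are the planned SVR12 confidence intervals mislabelled, given that a rate of exactly 95% cannot occur with 50 or 30 subjects?

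*Protocol*

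**What the plan says.** Protocol 8.7 supports the sample size by expected precision alone. The sizes are approximate: "For Cohort 1, with approximately 50 subjects enrolled into the study" and "For Cohort 2, with approximately 30 subjects enrolled into the study". The method is stated in full as "the 2-sided 95% exact CI using the binomial distribution (Clopper-Pearson method) of the SVR12 rate". For Cohort 1 the interval "will be from 86.3% to 99.5%, assuming the expected SVR12 rate is 95"%, and for Cohort 2 it "will be from 82.8% to 99.9%, assuming the expected SVR12 rate is 95"%. The Protocol Synopsis and SAP 1.3 repeat both intervals. None of the three places gives a number of responders, an observed proportion or a rounding rule.

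On how the result is used, Protocol 8.4.1 says "No hypothesis testing will be performed". It asks only for a point estimate and an exact interval by cohort, and SAP 6.1.2 asks for the same by genotype and overall within each treatment group.

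**The concern.** A Clopper-Pearson interval belongs to a whole number of responders out of n. At 95% the counts would be 47.5 of 50 and 28.5 of 30, so no such interval exists at exactly the assumed rate. The printed limits must therefore belong to some other observed rate, and the text does not say which. It also states the interval as something that will happen, although it is one possible outcome among several.

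Both counts turn out to be rounded up, the direction that gives the narrower interval. No power calculation is given, so these two intervals are the only figures offered in support of 50 and 30 subjects. If they were wrong or misleadingly narrow, a reader would have a false idea of the precision the trial can deliver, most of all in the smaller Cohort 2.

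**Working it through.** **Inputs** (Protocol 8.7): n = 50 and n = 30, both approximate; assumed SVR12 rate 95%; two-sided 95% Clopper-Pearson interval.

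**Formula.** For x responders of n, the lower limit is the 0.025 quantile of Beta(x, n − x + 1) and the upper limit is the 0.975 quantile of Beta(x + 1, n − x).

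**Step 1: reproduce the plan's figures.** 0.95 × 50 = 47.5 and 0.95 × 30 = 28.5. The whole counts on either side give:

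| Count | Observed rate | Lower | Upper | Width |
|---|---|---|---|---|
| 47/50 | 94.0% | 83.45 | 98.75 | 15.29 |
| 48/50 | 96.0% | 86.29 | 99.51 | 13.23 |
| 28/30 | 93.3% | 77.93 | 99.18 | 21.26 |
| 29/30 | 96.7% | 82.78 | 99.92 | 17.13 |

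The plan's 86.3% to 99.5% is 48/50, and its 82.8% to 99.9% is 29/30. A search over n from 40 to 60 and n from 24 to 36, allowing up to six failures, finds no other count that matches both limits to one decimal. Putting the fractional counts 47.5 and 28.5 into the formula gives 84.85 to 99.16 and 80.29 to 99.64, which is not what the plan prints. The figures therefore come from rounding a half up.

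**Step 2: are 48 and 29 reasonable planning outcomes?** Under a true rate of 95%:

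- Binomial(50, 0.95): P(X = 48) = 0.261 and P(X = 47) = 0.220. The mode and the median are both 48. P(X ≥ 48) = 0.541 and P(X < 48) = 0.459.
- Binomial(30, 0.95): P(X = 29) = 0.339 and P(X = 28) = 0.259. The mode and the median are both 29. P(X ≥ 29) = 0.554 and P(X < 29) = 0.446.

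The printed limits are thus those of the single most likely result and also of the median result. A lower limit at or above the printed one occurs 54% of the time in Cohort 1 and 55% in Cohort 2.

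**Step 3: how far off could a reader be?** The answer depends on the benchmark.

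- One responder fewer: the lower limit falls by 86.29 − 83.45 = 2.84 points in Cohort 1, and by 82.783 − 77.926 = 4.86 points in Cohort 2.
- Limits averaged over the binomial distribution at 95%: 85.07 to 98.87 (width 13.80) in Cohort 1 and 80.66 to 99.23 (width 18.57) in Cohort 2. The printed lower limits are higher by 86.29 − 85.07 = 1.22 and 82.78 − 80.66 = 2.12 points. The printed widths are smaller by 13.80 − 13.23 = 0.57 and 18.57 − 17.13 = 1.44 points.

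**Step 4: compare with the looseness already in the sample size.** Both sizes are approximate. Taking the whole count nearest to 95% at a nearby n moves the lower limit by similar amounts:

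| Count | Lower limit |
|---|---|
| 44/46 | 85.2% |
| 48/51 | 83.8% |
| 26/27 | 81.0% |
| 29/31 | 78.6% |

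The analysed number may also differ from the number enrolled, because SAP 3.1.2 restricts the Full Analysis Set to dosed subjects with detectable HCV RNA at baseline.

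**The case for a change.** The strongest case for a change is this. These intervals are the only quantitative support for the two sample sizes, they are attached to 95%, and they belong to 96.0% and 96.7%. The counts just below 95% are exactly as close to it as the counts used (47.5 is half a subject from both 47 and 48, and 28.5 from both 28 and 29). The plan shows only the narrower interval of each pair. In Cohort 2 the other one is 21.26 points wide instead of 17.13. Under a true 95% rate the lower limit falls below the printed value 46% of the time in Cohort 1 and 45% in Cohort 2, yet the sentence allows for no variation. Naming the counts would cost a few words in three places.

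The facts in this argument stand: the counts are not stated, and the verb is too definite. The inference that the figures are too favourable does not follow. A shortfall frequency just under one half is what any median outcome shows. The averaged interval is another defensible planning summary, but the plan never claims to report it. The sentence is also less absolute than its verb suggests, since it makes the size approximate and the rate an assumption. Nor is the reader left without means, because method, level, sidedness, size and both limits are printed and together lead back to 48/50 and 29/30.

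**Conclusion.** The observation is accurate, but no change follows. The limits are correct Clopper-Pearson intervals for 48/50 and 29/30. When 95% of n falls on a half, a whole count has to be chosen, and rounding up here picks the mode and the median under the assumed rate. What is missing is a note of the counts.

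That gap has no consequence for the trial. There is no hypothesis test, power figure, precision target or success threshold that a lower limit one to five points different would miss. SVR12 will be reported with an interval computed from the observed responders and the analysed number, so the planning interval does not enter any result. Writing the counts beside the limits would be tidier, but it would alter neither the sample size nor the analysis, and not the conclusions either.

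This rests on two assumptions: the limits were obtained by rounding the count up, which is the only reading found that reproduces them; and the planning intervals are used only to illustrate precision, as the documents indicate.

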8.8. Data Monitoring Committee

No data monitoring committee will be used in this study.

8.9. Endpoint Adjudication Committee

No Adjudication committee will be used in this study.

9. RESPONSIBILITIES

9.1. Investigator Responsibilities

9.1.1. Good Clinical Practice

The investigator will ensure that this study is conducted in accordance with ICH E6(R2) Good Clinical Practices and applicable laws and regulations.

9.1.2. Financial Disclosure

The investigator and sub-investigators will provide documentation of their financial interest or arrangements with Gilead, or proprietary interests in the investigational drug under study. This documentation must be provided prior to the investigator's (and any sub-investigator's) participation in the study. The investigator and sub-investigator agree to notify Gilead of any change in reportable interests during the study and for 1 year following completion of the study. Study completion is defined as the date when the last subject completes the protocol-defined activities.

9.1.3. Institutional Review Board (IRB)/Independent Ethics Committee (IEC) Review and Approval

The investigator (or sponsor as appropriate according to local regulations) will submit this protocol, informed consent form (ICF), and any accompanying material to be provided to the subject (such as advertisements, subject information sheets, or descriptions of the study used to obtain informed consent) to an IRB/IEC. The investigator will not begin any study subject activities until approval from the IRB/IEC has been documented and provided as a letter to the investigator.

Before implementation, the investigator will submit to and receive documented approval from the IRB/IEC any modifications made to the protocol or any accompanying material to be provided to the subject after initial approval, with the exception of those necessary to reduce immediate risk to study subjects.

